8.4. Weight

8.4.1. Absolute Value and Change from Baseline

The CFB in body weights will be calculated for each post-baseline visit. The analyses of body weights will be summarized descriptively in the same manner as described in Section 8.2.1.

8.5. Electrocardiogram

8.5.1. Absolute Value and Change from Baseline

The CFB in electrocardiogram (ECG) variables will be calculated for each post-baseline visit. The analyses of ECG will be summarized descriptively in the same manner as described in Section 8.2.1.

8.5.2. Shift in ECG

The shift analyses of ECG will be performed in the same manner as described in Section 8.2.2. ECG normal ranges are presented in Section 11.6.

8.5.3. Incidence of ECG

The number and percentage of subjects meeting the following criteria for any post-baseline value will be presented:

- QTcF: 450 to 480 msec (if male); 470 to 480 msec (if female); 480 to 500 msec; >500 msec
- CFB in QTcF: 30 to 60 msec; >60 msec.

8.6. Physical Examination

The number and percentage of subjects with Normal, Abnormal not Clinically Significant, Abnormal Clinically Significant and Not Done findings from CRF page will be summarized descriptively and flagged in the listings. Data listings will be provided.

8.7. Columbia Suicide Severity Rating Scales (C-SSRS)

C-SSRS includes combined suicidal ideation from 5 suicidal items (categories 1-5), combined behavior from 5 behaviors items (categories 6-10), overall suicidal ideation or behavior classification, and non-suicidal self-injurious behavior. The number and percentage of subjects with a response of “Yes” to each category of suicidal ideation and suicidal behavior will be presented by visit. The data listing for C-SSRS will be provided.

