7.3 Treatment-Emergent Suicidal Ideation

Prospective assessment of suicidal ideation and suicidal behavior is a mandatory part of the safety evaluations for any drug developed for a psychiatric indication ([US Food and Drug Administration 2012](#)). In this study, the initial evaluation of subjects will be conducted prior to enrollment to assess lifetime suicidal ideation and to identify subjects who must not participate in the study due to a pre-existing suicidality risk. The assessment will then be repeated at each

subsequent clinic visit as well as during the safety follow-up phone call to monitor the occurrence of new suicidal and self-injurious tendencies.

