7.3.1 Columbia Suicide Severity Rating Scale

Assessment of suicidal ideation and behavior will be conducted using the C-SSRS (Baseline/Screening Version and Since Last Visit Version) ([Posner 2011](#)). The C-SSRS is an FDA-recommended, prospective assessment instrument that directly classifies suicidal ideation and behavior events into 11 preferred categories, including 5 levels of suicidal ideation, 5 levels of suicidal behavior, and the category of self-injurious behaviors with no suicidal intent.

The instrument has been validated and used successfully in adult patients with various psychiatric disorders that do not involve cognitive impairment. The C-SSRS outcomes that can be used for clinical management and safety monitoring are suicidal lethality rating, suicidal ideation score, and suicidal ideation intensity rating.

The scale is a ClinRO administered by a qualified rater at screening, days 1, 4, 7, and 10 of the evaluation period, and during the safety follow-up phone call.

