8.13 Safety Analysis

Safety analysis is a secondary analysis and will be performed using the safety population. Summaries will be presented for TEAEs and data from the clinical laboratory tests, vital sign measurements, body weight, ECGs, C-SSRS, CADSS, and BPRS+. Physical examination results will be listed by subject.

TEAEs: The incidence rate for all TEAEs will be summarized for each System Organ Class (SOC) and Preferred Term (PT). The severity of the TEAEs, the relationship to SM, SAEs, AEs leading to SM withdrawn, and deaths will be summarized for each SOC and PT. Common TEAEs ($\geq 5\%$) will be summarized by PT. The verbatim descriptions with Medical Dictionary for Regulatory Activities coded SOCs and PTs for all AEs will be contained in the subject data listings.

Clinical Laboratory Values, Vital Sign Measurements, and Body Weight: Both actual values and change from baseline and shift from baseline will be summarized for clinical laboratory values, vital sign measurements, and body weight.

ECG results will be summarized using descriptive statistics (for quantitative ECG parameters) and frequency tables (for qualitative ECG parameters, including the overall ECG finding).

C-SSRS outcomes will be summarized using number and percentage of subjects by categories for suicidal ideation only, suicidal behavior only, and suicidality (ideation and behavior combined).

CADSS outcomes will be summarized using descriptive statistics.

BPRS+ outcomes will be summarized using descriptive statistics.

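### The planned C-SSRS summary counts Yes answers visit by visit, so it cannot show how many subjects had new or worsened suicidality after dosing, and its columns cover unequal look-back periods

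*SAP*

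**What the plan says.** Protocol 7.3, under a heading on treatment-emergent suicidal ideation, repeats the C-SSRS after enrollment "to monitor the occurrence of new suicidal and self-injurious tendencies". Protocol 7.3.1 has it "administered by a qualified rater at screening, days 1, 4, 7, and 10 of the evaluation period, and during the safety follow-up phone call". The Screening/Baseline version is used once, at screening. Every later assessment, including Day 1, uses the Since Last Visit version (Protocol Table 1).

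For analysis, SAP 8.7 gives the subjects answering Yes to "each category of suicidal ideation and suicidal behavior will be presented by visit". The only other output is a listing: "The data listing for C-SSRS will be provided". Protocol 8.13 plans counts for ideation, behavior and the two combined, and it gives no treatment-emergent rule. SAP 9 declares no change from the protocol.

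Protocol 6.4 allows the C-SSRS at unscheduled visits. SAP 3.1 excludes unscheduled measurements from summary tables unless another section says otherwise, and SAP 8.7 does not.

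**The concern.** The question that the protocol sets is about subjects: how many developed suicidal ideation or behavior, or got worse, after the first dose? The planned table answers a different one: how many were positive at each visit. The two differ because pre-dose ideation is to be expected. Exclusion 12 bars suicidal behavior and ideation of types 4 and 5 in the year before screening, but subjects with types 1 to 3 may enter. A type 1 answer at a subject's usual level and a new type 1 answer fall in the same cell. One subject positive at two visits cannot be told from two subjects positive at one visit each. A first Yes at an unscheduled visit does not reach the table at all.

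The columns also invite a comparison over time that they do not support, because the Since Last Visit form covers a different number of days at different visits.

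Suicidality is a named safety endpoint of an open-label depression study. At stake is a reliable count of emergent cases, and protection against reading a change of window as a change in patients.

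**Working it through.** The plan states no figure to reproduce. The sample size (about 50 enrolled, about 40 completing) rests on clinical judgment, and no ideation rate is given.

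**1. What visit counts can identify.** Take 50 subjects, 5 positive on Day 1, and 5 positive at each of the four later contacts (Days 4, 7, 10 and the call). These counts are illustrative.
- Fewest newly positive: the same 5 subjects throughout, so 0.
- Most newly positive: 5 different subjects each time, all negative on Day 1, so 4 × 5 = 20 (within the 45 negatives).

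Identical tables are compatible with 0 or 20 emergent cases.

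**2. How the SAP treats other safety data.**
- Laboratory shift tables run to the worst post-baseline value, including unscheduled visits (8.2.2). Vital sign and ECG shifts follow the same method (8.3.2, 8.5.2).
- Clinically notable laboratory values use a denominator of subjects without a notable value at baseline (8.2.3).
- QTcF categories count any post-baseline value (8.5.3).

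The C-SSRS has no equivalent of any of these.

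**3. Look-backs from the calendar.**

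| Contact | Source | Look-back |
|---|---|---|
| Screening | Protocol 7.3 | lifetime |
| Day 1 | screening on Day -28 to -1; SAP Table 2 day count | 1 to 28 days |
| Days 4, 7, 10 | 4 − 1, 7 − 4, 10 − 7 | 3 days each |
| Call | Day 12 (+2): 12 − 10 to 14 − 10 | 2 to 4 days |

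The call row uses the +2 window of Table 1; Protocol 4.3 prints ±2. Protocol 4.1 also places the C-SSRS in the home calls on Days 2, 3, 5, 6, 8 and 9, while Table 1 and Sections 6.2.1 and 7.3.1 do not. If the home calls include it, the look-backs through Day 10 become about 1 day.

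**4. What unequal windows can do.** Assume a constant episode rate with no drug effect, a share p = 30% positive on Day 1, and one Day 1 look-back T for everyone. Both p and T are assumptions. The expected share positive over 3 days is 1 − (1 − p)^(3/T).

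| T (days) | Day 1 | 3-day visit | Of 50 subjects |
|---|---|---|---|
| 28 | 30% | 3.7% | 15 → 1.9 |
| 14 | 30% | 7.4% | 15 → 3.7 |
| 7 | 30% | 14.2% | 15 → 7.1 |
| 3 | 30% | 30% | 15 → 15 |
| 1 | 30% | 65.7% | 15 → 32.9 |

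Now let a share q of the Day 1 positives have persistent ideation, always positive, with T = 28. The episodic rate among the rest is e = (p − qp)/(1 − qp), and the 3-day share is qp + (1 − qp)[1 − (1 − e)^(3/28)]. For q = 0.5: qp = 0.15, e = 0.15/0.85 = 0.176, and the result is about 17% (8.4 of 50). For q = 0.25 it is 10.2%, for q = 0.75 it is 23.3%, and for q = 1 it is 30%, with no fall.

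**The case against.** A reader might infer that the table is bound to show a spurious fall in suicidality. The documents do not support that. The Day 1 look-back runs from 1 to 28 days and varies by subject. At 3 days there is no fall, below 3 days the direction reverses, and with persistent ideation there is no fall at any look-back. Nor does the 28:3 ratio of maximum windows measure the effect, because no ideation rate is given. The most serious rows are little affected: exclusion 12 leaves behavior and types 4 and 5 near zero before dosing, so they have little room to fall, and a post-dose Yes there is visible. A move from type 2 to type 4 also lands in a different row.

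A reader might also infer that new cases would be lost. They would not. The listing shows them subject by subject. A condition that worsens after dosing is entered as a new adverse event (SAP 8.1), and clinically significant suicidal ideation or behavior goes to drug safety within 24 hours (Protocol 7.2.10). SAP 3.6 sets no hypotheses, and SAP 8.7 plans no formal comparison of Day 1 with later visits.

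All of this stands, and it limits the artifact. It does not supply the missing count. Adverse event tables depend on what the investigator records as an event, not on scale categories. A count taken from the listing afterwards needs a choice of pre-dose reference, either the lifetime screening form or the Day 1 form, and the SAP does not make that choice before the data are seen.

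**Conclusion.** The point holds in two parts of unequal strength. The firm part is that the only planned C-SSRS summary cannot give the number of subjects with new or worsened ideation or behavior, which is what Protocol 7.3 says the scale monitors, and that it omits unscheduled assessments. This follows from the text and needs no assumption about rates; the 0 to 20 range illustrates it.

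The conditional part is that ideation of types 1 to 3 can appear to fall after Day 1 without a drug effect. This requires a Day 1 look-back above about 3 days and ideation that is at least partly episodic. Under the assumptions shown, a 30% share on Day 1 could become anything from 3.7% to 30% for look-backs of 3 to 28 days. The true size is unknown. The 3-day figure also depends on how the home-call conflict is resolved.

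The consequence is for descriptive safety interpretation, not for error rates or the primary endpoint. It should be corrected before database lock.

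**What to change.** In SAP 8.7, keep the by-visit table and add the following for the Safety Population, expressly including unscheduled assessments:

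- (a) n (%) with any post-baseline ideation, behavior, either of these, and non-suicidal self-injury;
- (b) n (%) treatment-emergent, meaning a highest post-dose category above the highest pre-dose category. The prespecified reference is the Day 1 pre-dose Since Last Visit form, which is the baseline under SAP Table 2. A sensitivity count adds the screening form to the reference;
- (c) a shift table of highest pre-dose against highest post-dose category.

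Footnote each visit column with its look-back, and state that Day 1 and later columns are not directly comparable. Reconcile Protocol 4.1 with Table 1 and Sections 6.2.1 and 7.3.1 on the C-SSRS in home calls, because this sets the later look-backs.

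The cost is some programming; no new data are needed. There is one limitation to state with the results. The post-dose period is about 11 to 13 days (12 − 1 to 14 − 1), while the Day 1 look-back can reach 28. A longer pre-dose window raises the reference and can understate emergence, and adding the lifetime screening form raises it further. A very short Day 1 look-back can do the opposite.

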8.8. CADSS and BRPS+

The CADSS is a 23-item clinician administered scale that measures present-state dissociative symptoms. The subject then rates items on a 4-point Likert scale as follows:

- a. 0 = not at all
- b. 1 = mild
- c. 2 = moderate
- d. 3 = severe
- e. 4 = extreme

The total score ranging from 0 – 92 is the sum of the 23 items.

The Brief Psychiatric Rating Scale (BPRS+) is a tool clinicians or researchers uses to measure psychiatric symptoms such as anxiety, depression, and psychoses. For the study, the version used is adapted from the original BPRS 4-item positive symptoms (BPRS+). The scale is comprised of 4 items assessing a subject’s experience of psychosis, often referred as positive symptoms of Suspiciousness, Hallucinatory Behavior, Unusual Thought Content and Conceptual Disorganization. Of the 4 items assessed, the first three items are based on questions asked by the clinician to the subject, Conceptual Disorganization is a clinician rated item based on observation of subjects’ behavior and speech during the assessment. Each subscale is rated on a 7-point scale ranging from 0-7 as follows:

- a. 0 = not able to be assessed
- b. 1 = not present
- c. 2 = very mild
- d. 3 = mild

- e. 4 = moderate
- f. 5 = moderately severe
- g. 6 = severe
- h. 7 = extremely severe

The total score ranging from 0-28 is the sum of the 7 items.

Descriptive statistics will be presented for CADSS total score, and BPRS+ scores by visit.

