8.3 Handling of Dropout or Missing Data

For safety analyses, a missing date for an AE and non-study medication use will be imputed as described in the SAP. Missing data for all other safety endpoints will not be imputed.

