3. GENERAL CONSIDERATIONS FOR DATA ANALYSES AND HANDLING

3.1. General Statistical Methods

All statistical analysis will be performed using SAS version 9.4 or higher. All data will be summarized for the SPN-820 treatment group.

Continuous variables will be summarized descriptively using number of subjects (n), mean, standard deviation (SD), median, first quartile (Q1), third quartile (Q3), minimum, and maximum.

Categorical variables will be summarized descriptively using counts and percentages. When the denominator for the percentage is different from the number of subjects in the treatment column header of a summary table, the denominator will be specified in a footnote for the table.

Individual subject data will be listed by subject ID. Unscheduled measurements (unless defined as baseline or otherwise specified) will be excluded from summary tables but will be included in data listings. For assessments that are repeated or unscheduled for a visit, unless otherwise specified, the non-missing values from the first assessment will be used for generating summary statistics.

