5.1. Primary Efficacy Endpoint

The Hamilton depression rating scale is one of the most widely used clinician-administered depression scales. The original version contains 17 items related to symptoms of depression over the past week developed for hospital inpatients. The HAM-D₆, a subscale version with 6 items derived from the 17 items of the original scale, offers sensitivity for measuring severity of detecting improvement of depression comparable to other more complex versions. Five of the 6 items (Depressed Mood, Work and Activities, Feeling of Guilt, Anxiety Psychic, and Retardation) are scored on a scale of 0 to 4, and 1 item (Somatic Symptoms General) is scored on a scale of 0 to 2, for a possible total score of 0 to 22. If any item score is missing, the total score will not be calculated. A total score ranging 0-4 indicates that the subject is in the normal range (no depression), a score ranging 5-8 indicates “mild depression”, 9-12 indicates “moderate depression”, and 13-22 indicates “severe depression”.

CFB in the HAM-D₆ total score will be analyzed descriptively at each time point using the FAS.

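### The BPRS+ total range of 0-28 in SAP 8.8 is reachable only if the code for an unassessable item is summed as a score

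*SAP*

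**What the plan says.** SAP section 8.8 says of the BPRS+ that "The scale is comprised of 4 items", and Protocol section 7.2.13 gives the same number. On item scoring the SAP says: "Each subscale is rated on a 7-point scale ranging from 0-7 as follows". In the list that follows, the lowest code is "0 = not able to be assessed", code 1 means the symptom is absent, and code 7 is the most severe rating. The total is then defined: "The total score ranging from 0-28 is the sum of the 7 items".

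On use of the score, the same section says: "Descriptive statistics will be presented for CADSS total score, and BPRS+ scores by visit". Under SAP section 3.1 the summary statistics are the usual ones: "Continuous variables will be summarized descriptively using number of subjects (n), mean, standard deviation (SD), median", followed by quartiles, minimum and maximum.

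On missing data, Protocol section 8.3 covers safety endpoints other than AE and medication dates: "Missing data for all other safety endpoints will not be imputed". SAP section 5.1 has an item-level rule for HAM-D6, "If any item score is missing, the total score will not be calculated", and section 5.2 repeats it for MADRS. Section 8.8 has no such rule for the BPRS+.

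**The concern.** Code 0 is not a degree of severity. It records that no rating could be made. A stated minimum of 0 tells the programmer to add that code into the total as if it were a score one step below an absent symptom.

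The error runs in the wrong direction for a safety scale. An item that could not be rated can only make the subject look less ill. In effect the missing rating is replaced by a value below the scale's floor, which sits badly with the no-imputation statement in Protocol section 8.3.

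There is one visit where code 0 could foreseeably be used. The BPRS+ is also given at the Day 12 safety phone call (Protocol sections 6.3 and 7.2.13), and Conceptual Disorganization is rated from observed behavior and speech. Speech can be heard by telephone but behavior cannot be seen. The documents do not say that raters will use 0 there. If they did so routinely, Day 12 totals would drop for a reason unrelated to the subjects' condition.

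**Working it through.** **Inputs**

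- Items: 4 (SAP 8.8; Protocol 7.2.13).
- Item codes: 0 to 7, with 0 = not assessable, 1 = symptom absent, 7 = most severe (SAP 8.8).
- Stated total: 0-28, as a sum of 7 items (SAP 8.8).
- Subjects at a visit: 40 to 50. This is an assumption, taken from the planned completers and enrolment in SAP 2.6.

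**Reproducing the stated range**

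Range of a sum = (items x lowest code) to (items x highest code).

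| Reading | Minimum | Maximum |
|---|---|---|
| 4 items, codes 0-7 | 4 x 0 = 0 | 4 x 7 = 28 |
| 4 items, ratings 1-7 only | 4 x 1 = 4 | 4 x 7 = 28 |
| 7 items, codes 0-7 | 7 x 0 = 0 | 7 x 7 = 49 |
| 7 items, ratings 1-7 only | 7 x 1 = 7 | 7 x 7 = 49 |

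The stated 0-28 is exactly the first row: 4 items with code 0 counted as a score. The figure of 7 items is a slip, since 28 = 4 x 7. Seven items scored 0-4 would also give 0-28, but that contradicts both the item count and the codes in the same section. The upper limit of 28 is right; only the lower end is wrong.

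**Totals that need code 0**

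If every item is at least 1, the sum is at least 4. Enumerating all 8^4 code patterns confirms this: totals of 0, 1, 2 and 3 arise from 1, 4, 10 and 20 patterns, and every one contains at least one 0.

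**Effect on one subject**

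- An unassessable item whose true rating is r lowers the total by r, so by 1 to 7 points.
- A symptom-free subject with k unassessable items scores 4 - k: 3, 2, 1 or 0 for k = 1, 2, 3 or 4, instead of 4.
- Three items rated moderate (4) and one unassessable give 3 x 4 + 0 = 12, the same as four items rated mild, 4 x 3 = 12.

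**Effect on a visit mean**

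Shift from one unassessable item = r / n.

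- Smallest: 1/50 = 0.02.
- Largest: 7/40 = 0.175. This is a ceiling, since it needs a true rating at the top of a psychosis item in a study that excludes lifetime psychotic disorder.
- If one item were unassessable for every subject at a visit, the mean would fall by at least 1 point, because each subject loses at least 1.

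**Would the table minimum show it?**

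Only if a total falls below 4. With exactly one 0 there are 4 x 7^3 = 1,372 patterns. The total is below 4 only when the other three items are all 1, which is 4 patterns; the other 1,368 lie within 4-28. These are counts of patterns, not expected frequencies. In a mostly symptom-free sample the 4 visible patterns would be the common ones.

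**CADSS, for comparison**

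In the same section CADSS has 23 items coded 0-4, where 0 is a real score for no symptom. Its range of 23 x 0 = 0 to 23 x 4 = 92 is correct.

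**The case against.** The best opposing case accepts the contradiction and argues that little follows from it.

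- **Little depends on the score.** The study is open-label with a single group, no hypotheses, no subgroups and no interim analysis, and no decision rule uses the BPRS+ total. This is true and limits the consequence. It does not make the scoring rule right.
- **The listings would show it.** Protocol section 8.1 promises a listing of all eCRF data and SAP section 3.1 lists individual data. If item ratings are on the eCRF, a code 0 would be visible there, so the table minimum is not the only place to look. This stands, but a listing does not correct a mean in a summary table.
- **Protocol section 8.3 already forbids imputation.** If an unassessable item counts as missing, summing it as 0 would breach that section. No text makes that classification, however, and the stated range of 0-28 implies the opposite. This mitigates without curing.
- **The point count proves little.** A 7-point scale running from 0 to 7 has eight codes, which might suggest that 0 is not a rating. But the same section calls the five CADSS codes a 4-point scale, and there 0 is a genuine score. The wording is loose, so this is weak support at most. The conclusion rests on the code labels and the stated range.
- **Withholding the total is one option among several.** Summarizing the items separately would also be defensible, and the planned BPRS+ scores may already include them. That is fair. The proposed rule has the advantage that the SAP already uses it for HAM-D6 and MADRS.

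**Conclusion.** The concern holds. SAP section 8.8 states a total range that contradicts its own item coding. With 4 items rated 1-7 the range is 4-28, and the stated minimum of 0 requires the non-assessment code to be summed. Neither document recodes 0 as missing for this scale.

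The bias is always downward. Its size in the trial depends on how often code 0 is recorded, which the documents do not give. With isolated use the effect on a visit mean is small; with systematic use at one visit it would be at least 1 point on a scale whose floor is 4. This is a correction the sponsor should make to a listed safety endpoint. It does not touch the primary analysis.

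**What to change.** Replace the total-score sentence in SAP section 8.8 with text such as:

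> Each BPRS+ item is rated 1 to 7. The BPRS+ total is the sum of the 4 items, range 4-28. A code of 0 denotes an item that could not be assessed and is treated as missing; no total is derived when any of the 4 items is missing.

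Correct the description of the item scale to match. Report the number of unassessable ratings at each visit, and confirm that the listings show item-level ratings, so that subjects without a total remain visible.

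The cost is two or three sentences, one count per visit, and an item-level listing that the Protocol's listing commitment may already cover. The drawback is that a few totals become missing, which could take an affected subject out of a visit summary. If code 0 were routine at the Day 12 call, many totals there could be lost, and the count by visit would show it.

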3.2.4 Safety Endpoints

- TEAEs.
- Clinical safety laboratory test results.
- Vital sign measurements including orthostatic blood pressure and pulse rate.

- Body weight.
- Electrocardiography (ECG) findings.
- Physical examination findings.
- Suicidal ideation and behavior as measured by the Columbia Suicide Severity Rating Scale (C-SSRS) score.
- Dissociative symptomatology as measured by the Clinician-Administered Dissociative State Scale (CADSS) score.
- Psychopathology severity as measured by the Brief Psychiatric Rating Scale Positive Subscale (BPRS+) score.

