- The follow-up assessments will be performed through a safety follow-up phone call. The safety follow-up phone call will occur approximately 5 days after the last administration of SM.
- AEs reported during screening will be recorded as part of the subject's medical history.
- A complete physical examination will be performed at screening and baseline visits; a brief physical examination will be performed at EOS/ET.
- Vital signs measurements include orthostatic blood pressure/pulse rate, respiratory rate, and oral temperature. Orthostatic blood pressure and pulse rate should be measured after the subject has been sitting for 5 minutes and again within 3 minutes of subject standing.
- ECGs should be performed prior to blood draws.
- Serology tests include human immunodeficiency 1/2 antigen/antibody, hepatitis B surface antigen, and hepatitis C virus antibody.
- A standard urine drug screen will be performed at screening and point-of-care urine drug screen together with the breathalyzer will be performed at baseline (Day 1) and all post-baseline clinic visits (days 4, 7, and 10).
- On days 2, 3, 5, 6, 8, and 9, the HAM-D₆ questionnaire will be administered remotely by telephone.
- SAEs will be captured from the time of ICF signing, and AEs will be captured following the first administration of SM and continue through the FPC.
- Seven total blood samples will be collected for measurement of BDNF concentrations: 3 pre-dose collections on days 1, 4 and 7; 3 post-dose collections 4 hours after SM administration on days 1, 4, and 7; and 1 collection on Day 10.
- Subjects will take their SM in the clinic.
- Subjects will receive a paper ADT adherence diary at screening and document the day of each dose of their ADT throughout the study. Subjects will bring their ADT adherence

diaries to each clinic visit for review of subject compliance.

m. ADT will not be provided by the Sponsor. Subject's ADT will have started and have been stable for at least 6 weeks prior to screening and will continue through the safety follow-up phone call.

Table 2: Detailed Schedule of Timed Assessments (Window)

Study Day	Clinic Visit Number	Location	Time ^a		HAM-D ₆ ^b	MADRS ^b	CGI-S	BDNF ^c
1	2	Clinic	Pre-dose		X (-60 min)	X (-60 min)	X (-60 min)	X (-60 min)
			1 hour					
			2 hours		X (±30 min)			
			4 hours		X (±30 min)	X (±30 min)		X (±30 min)
			8 hours		X (±30 min)			
2	–	Home	24 hours		X (±2 h) ^e			
3	–	Home	48 hours		X (±2 h) ^f			

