6.3 Safety Follow-Up Phone Call (Day 12)

Subjects who complete EOS/Study Day 10 will receive a safety follow-up phone call approximately 5 days (+2 days) after the administration of SM on Day 7.

The following assessments will be conducted:

- Administer safety assessments (C-SSRS [Since Last Visit Version], CADSS, and BPRS+ scales)
- Review AEs
- Review concomitant medications

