7.2.13 Brief Psychiatric Rating Scale

The BPRS is one of the most widely used instruments enabling the clinician to quickly gather information about the possible presence and severity of various psychiatric symptoms ([Zanello 2013](#)). Varying in the number and type of symptoms assessed, clarity of anchor point definitions and administration and rating instructions, the BPRS exists in various forms. Originally in the early 1960s, the BPRS was developed as a 16-item instrument ([Overall 1962](#)), that was later extended to 18 items and was used for many years ([Overall 1967](#)). In order to increase its sensitivity to psychotic and affective disorders as well as to be used with patients living in the community, the BPRS was expanded to 24 items (Version 2, [Lukoff 1986](#)). In its latest version (Version 4.0), the manual of administration of the 24-item BPRS+ ([Ventura 1993](#)) not only offers a more detailed semi-structured interview containing more probe questions for each symptom but also provides supplementary rules for the rating (e.g., delusions) with better-defined anchor points.

The version used for this study is adapted from the original BPRS+. The scale is comprised of 4 items assessing a subject's experience of psychosis, often referred to as positive symptoms of Suspiciousness, Hallucinatory Behavior, Unusual Thought Content, and Conceptual Disorganization. Of the 4 items assessed, the first 3 items are based on questions asked by the clinician to the subject. Conceptual Disorganization is a clinician-rated item based on observation of a subject's behavior and speech during the assessment.

The scale is a ClinRO administered by a qualified rater at screening, days 1, 7, and 10 of the evaluation period, and during the safety follow-up phone call.

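### SAP 8.8 adds the BPRS+ code for an item that could not be assessed (0) into the total as if it were milder than symptom absent (1)

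*SAP*

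**What the plan says.** Protocol 3.2.4 lists the endpoint as "Psychopathology severity as measured by the Brief Psychiatric Rating Scale Positive Subscale (BPRS+) score", and words the CADSS endpoint in the same way. Protocol 8.13 promises descriptive statistics for both scales and nothing more specific. SAP 8.8 makes this concrete: "Descriptive statistics will be presented for CADSS total score, and BPRS+ scores by visit".

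The scoring rule for BPRS+ is found only in SAP 8.8. That section names four items: suspiciousness, hallucinatory behavior, unusual thought content and conceptual disorganization. It introduces the item codes with "Each subscale is rated on a 7-point scale ranging from 0-7 as follows", then lists eight codes. The lowest is "0 = not able to be assessed"; code 1 means the symptom is absent and code 7 is the most severe. The total is then defined: "The total score ranging from 0-28 is the sum of the 7 items".

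Protocol 7.2.13 describes the same four items but gives neither item codes nor a total. Protocol 8.3 says that, apart from certain dates, missing safety data are not imputed. SAP 5.1 and 5.2 leave the HAM-D6 and MADRS totals uncalculated when an item is missing; SAP 8.8 has no such rule.

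**The concern.** A code that records the absence of a rating is not a severity level. Adding it as 0 places an unassessed item below a symptom-free one, so a subject who could not be rated looks healthier than one rated free of psychotic symptoms. BPRS+ is a named safety endpoint in a single-arm study, where the subject's own earlier rating is the only internal reference. A scoring rule that moves totals for reasons unrelated to symptoms spoils exactly that comparison. Any summary of the item scores that keeps the zeros has the same fault.

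A lesser matter sits beside it. The SAP writes out change from baseline for laboratory values, vital signs, weight, ECG, the efficacy scales and BDNF, but not for CADSS or BPRS+. By-visit tables of raw scores do not show the spread of within-subject change, or how many subjects are above their own baseline.

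**Working it through.** **1. Reproduce the stated range.** Inputs from SAP 8.8: four named items, codes 0 to 7, stated range 0-28.

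- Four items, codes 0-7: 4 × 0 = 0 to 4 × 7 = 28. This matches.
- Seven items, codes 0-7: 0 to 7 × 7 = 49. This does not match.
- Four items, severity codes 1-7: 4 × 1 = 4 to 4 × 7 = 28.

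So the number seven is a slip for four. The lower limit of 0, however, needs all four items to carry the non-assessment code, so the stated rule does add that code. As a contrast, the CADSS total is 23 items coded 0-4, giving 0 to 23 × 4 = 92 as stated. There 0 means the symptom is absent, and the problem does not arise.

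**2. Effect on one subject.** An item whose true rating is between 1 and 7 but is recorded as 0 makes the total too low by 1 to 7 points. A symptom-free subject totals 4 when fully assessed, and 3, 2, 1 or 0 with one, two, three or four items not assessed.

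| First visit | Later visit | Totals | What the table shows |
|---|---|---|---|
| 1,1,1,0 | 1,1,1,1 | 3 to 4 | false worsening |
| 1,1,1,1 | 1,1,1,0 | 4 to 3 | false improvement |
| 1,1,1,1 | 2,1,1,0 | 4 to 4 | new symptom hidden |
| 1,1,1,1 | 4,0,0,0 | 4 to 4 | moderate symptom hidden |

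**3. Effect on a visit mean.** The documents give no frequency for code 0, so the counts here are assumed. If m of n otherwise symptom-free subjects have k items coded 0, the mean total is 4 − mk/n. The sample sizes are the planned 50 enrolled and 40 completing.

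| m | k | n = 50 | n = 40 |
|---|---|---|---|
| 0 | – | 4.00 | 4.00 |
| 1 | 1 | 3.98 | 3.975 |
| 5 | 1 | 3.90 | 3.875 |
| 1 | 4 | 3.92 | 3.90 |
| 5 | 4 | 3.60 | 3.50 |

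The shift in the mean is modest under these counts. The harm lies more in single subjects' totals, and in a minimum that can fall below the scale's true floor of 4.

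**4. What by-visit tables omit.** Assumed CADSS data: 50 subjects, five scoring 10 and the rest 0, at baseline and again at one later visit. At each visit the mean is 50/50 = 1.0 and the SD is √[(5 × 81 + 45 × 1)/49] = 3.03, whoever the five are. If u subjects rise and u fall, the SD of change is √(200u/49).

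- Same five subjects (u = 0): none above baseline, SD of change 0.
- Three in common (u = 2): two above baseline, SD of change 2.86.
- None in common (u = 5): five above baseline, SD of change 4.52.

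The raw tables are identical in all three cases. If every baseline is 0, the change equals the score and nothing is lost.

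**The case against.** The case for leaving the section alone has several parts.

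- **The seven is a plain typing error.** This stands: the same section lists four items and the maximum is 28, so a programmer is unlikely to be misled. It does not rescue the lower limit of 0.
- **Protocol 8.3 already bars imputation.** It does, and that supports treating 0 as missing. But SAP 8.8 is the text that will be programmed. Its range tells the programmer to add the zeros, and SAP 9 declares no departure from the protocol.
- **The plan refers to BPRS+ scores, which may include item scores.** Zeros would then be visible, as they would be in the listings. That helps a reader detect the problem but leaves the total wrong.
- **Raw scores by visit are what was promised.** This stands. A reader might infer that omitting change from baseline breaks a commitment. It does not: the endpoints are worded as scores and the protocol offers only descriptive statistics. By-visit tables include the median, quartiles and extremes, individual scores are listed, and symptoms reported as adverse events are counted per subject. Protocol 4.2.3 excludes lifetime psychotic disorder, recent PTSD or acute stress disorder, and cluster A or B personality disorder, so baselines near floor are plausible and the loss may be small.

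A reader might also infer that Day 12 will yield many zeros, since Protocol Table 1 notes that "The follow-up assessments will be performed through a safety follow-up phone call" and conceptual disorganization is rated by observing the subject. The documents do not support that. The item draws on speech as well as behavior, and speech can be judged by telephone. No expected rate of unassessable ratings is given for any visit.

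**Conclusion.** The BPRS+ total in SAP 8.8 is mis-specified and should be corrected before its tables are programmed. This follows from the SAP's own codes and range and needs no outside assumption: the total should run 4-28, and each item coded 0 puts it 1 to 7 points too low. The effect on reported results depends entirely on how often code 0 is used. If it is never used, nothing changes; with five of 50 symptom-free subjects each having one such item, the visit mean falls from 4.0 to 3.9. The error threatens neither the design nor the efficacy analysis.

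The missing change from baseline for CADSS and BPRS+ is a gap worth closing at little cost, but it is not an error. Its value depends on baseline distributions that the documents do not give.

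**What to change.** **Correction, in SAP 8.8.** Define the BPRS+ total as the sum of four items, range 4-28, with severity codes 1-7. Treat an item coded 0 as missing, in line with Protocol 8.3, and do not calculate the total when any item is missing, as SAP 5.1 and 5.2 already do for HAM-D6 and MADRS. Leave 0 out of item summaries. Report by visit how many totals were not calculated, and keep the original codes in the listings.

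The cost is a few sentences and some lost totals. If subjects are unassessable because of their condition, the lost totals are not a random subset, which is why their number should be shown.

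**Optional addition.** Give change from baseline by visit for the CADSS and BPRS+ totals, using the SAP Table 2 baseline, with n (%) above, equal to and below the subject's own baseline among those with both values. This takes about one table per scale from data already collected. Footnote that the counts include chance variation. For example, if 10% of CADSS ratings were nonzero independently at each visit, 50 × 0.10 × 0.90 = 4.5 subjects would be expected to go from zero to nonzero with no true change, and as many the other way. The counts above and below should be read together, and neither shows a drug effect in one arm. The scoring correction should come first, since a change score would inherit the error.
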